been significant advancements in the understanding of how inflammation contributes to the pathogenesis and progression of HF. It has long been observed that heart failure (HF) is associated with measures of systemic inflammation. However although numerous studies have validated the association between measures of inflammation and HF severity and prognosis, clinical trials of anti-inflammatory therapies have proven mostly unsuccessful with introduction of new clinical tries of anti-inflammatory therapy discussing its effect on the progression of heart failure (Sean et al., 2020).

ST2 is a member of the Toll-like/interleukin (IL)-1 receptor super family. Due to its cell-signaling capacities, IL-1 plays a central role in the regulation of immune and inflammatory responses and is linked to the processes of infection and inflammation. Through alternative splicing, there are 2 isoforms of ST2: a soluble or serum circulating receptor ST2 (sST2) and a transmembrane receptor ST2 ligand (ST2L) (*Pascual-Figal and Januzzi 2015*).

The expression of sST2 is largely inducible and almost ubiquitous in living cells, such as resting fibroblasts. It has been suggested that sST2 is produced by both cardiac fibroblasts and cardiomyocytes in response to injury or stress, and by macrovascular (aortic and coronary artery) and heart microvascular endothelial cells in response to diastolic load *(Ghashghaei et al., 2016)*.

Soluble ST2 has been evaluated in a number of clinical cardiovascular diseases CVD studies and is a Food and Drug Administration (FDA) approved prognostic biomarker of mortality in chronic heart failure patients. Previous meta-analyses have shown that sST2 has diagnostic value for heart failure and is prognostic for

all-cause mortality in heart failure, coronary artery disease and following aortic valve replacement. However, there is a paucity of clinical studies on IL-33, which is likely due to difficultly measuring circulating levels (*Liu et al., 2020*).

HF patients are often elderly and have many comorbidities, thus they are a challenging population to provide exercise training to. These patients have often been sedentary for a very long time, with a frequent motion-limiting comorbidities. Exercise in heart failure increases the ability to perform sub-maximal activities in daily life, improving quality of life by implementation of different types of exercise (*Beckers and Gevert 2020*).

Aerobic exercises can be continuous, of moderate intensity or intercalating high and low-intensity efforts. High-intensity interval training (HIIT) is currently one of the most effective methods for improving cardiorespiratory and metabolic function. HIIT involves repeated activities, from short to long ones, of high-intensity exercises combined with periods of active or passive recovery (*Tschakert and Hofmann 2013*).

Moderate-intensity continuous training (MICT) is regarded as a successful approach to CR because of its efficacy and safety. Some studies found that MICT can reduce cardiovascular risk and cardiovascular mortality. MICT entails longer durations of moderate-intensity continuous aerobic activity, maintaining intensity between 60 and 80% (VO2peak or reserve heart rate) (Yue et al.,2022).

Recently reported that HIIT is superior to traditional continuous aerobic training in improving cardiac autonomic function and suggested that the effect verified on post-HIIT autonomic

function was related to improve bar reflex modulation and vagal control (*Kiviniemi et al. 2014*).

Several studies reported exercise-induced Moderate Intensity Continuous Training (MICT) favorable cardiac chambers remodeling in post-infarction and in heart failure (either with reduced or preserved ejection fraction) patients (Mueller et al., 2021).

Statement of the Problem:

Is there a significant difference between high intensity interval training versus moderate intensity continuous training on soluble ST2 biomarkers in chronic heart failure?

The Purpose of the Study:

To determine the effect of high intensity interval training versus moderate intensity continuous training on soluble ST2 biomarkers in chronic heart failure.

Significance of the Study:

A recent study of incident HF conducted between 1998 and 2017 in the United Kingdom (UK), age-adjusted rates of first hospitalizations increased by 28% for both all-cause and HF admissions, and by 42% for non-CV admissions. The risk of HF hospitalization is 1.5 times higher in patients with diabetes compared to controls. AF, a higher body mass index (BMI), and higher glycated haemoglobin (HbA1c), as well as a low estimated glomerular filtration rate (eGFR) are strong predictors of HF hospitalizations (Lawson et al., 2019).

Biomarkers have made a significant contribution to the diagnosis and prognosis of disease. Although strongly associated with

inflammatory and autoimmune diseases, ST2 has also been found to play a role in the diagnosis and prognosis of CVD. As one of the isoforms of ST2, sST2 has recently become a promising prognostic indicator for patients diagnosed with HF and a useful tool for risk stratification. Due to its prognostic value, sST2 was recommended by the American College of Cardiology Foundation (ACC)/American Heart Association (AHA) as an important biomarker for monitoring HF patients in 2013 (Zhang et al., 2021).

Several systematic reviews have compared the effectiveness of high intensity interval training (HIIT) and moderate intensity continuous training (MICT) in HF patients. All these studies investigated the changes of VO2peak in HIIT when compared with MICT. However, limited by a few numbers of included studies or a mixture of heart failure in CAD patients, the conclusion was constrained with high heterogeneity. In addition, regarding health outcomes such as other cardiorespiratory parameters, cardiovascular risk factors, left ventricular function and quality of life, there is a lack of investigations and the existing results remain inconsistent *(Elliott et al., 2015)*.

A systematic review and meta-analysis included the latest RCTs aims to evaluate the broad-spectrum physical health benefits of HIIT compared with MICT, with a specific focus on cardiorespiratory fitness, heart rate, blood pressure, blood lipids, left ventricular function and QoL in CAD patients without reduced LVEF or heart failure (Xie et al., 2017).

A comprehensive review of the relevant literature is needed to resolve these limitations and determine the efficacy of HIIT versus MICT in HF patients. This would be helpful to develop a more targeted and efficient exercise prescription and contribute to more alterative choices in CR management (*Liou et al., 2016*).

The current study is expected to add important knowledge on the pathophysiology of HF and the clinical benefits of a training intervention as a novel treatment strategy in HF patients, which may help to improve both quality of life (QoL) and functional status in affected patients.

Delimitations:

This study will be delimited to the following aspects:

Subjects:

Sixty male patients with chronic heart failure grade \circ NYHA I, II.

Patients will be divided into two groups group A or receiving HIITS and group B receiving MICT.

Patients are ready to participate and cooperate actively in our exercise program.

Patients who will meet one of the following criteria are to obe excluded from the study:

Signs of acute heart failure, unstable angina or severe .1 arrhythmia three months prior to enrolment in the study.

Pacemakers. .2

.3

Chronic obstructive pulmonary disease.

Other disorders counteracting exercise testing conditions .4 that limit lower limb mobility (for example, burns, fractures)

Pre-existing neuromuscular diseases (for example .5 neuromuscular disorder).

Basic Assumptions:

It will be assumed that:

- 1. The primary medical assessment will be done to every participating patient which includes:
- -Complete medical history (personal, present and past)
- Referral from the physician.
- -homodynamic stability without need for vasoactive drugs.
- 2. All patients will stick to the program and will follow instructions.
- 3. All other factors which may influence the outcome such as noise and distraction will be controlled.

Hypothesis:

It will be hypothesized that there will be a significant difference between high intensity interval training and moderate intensity continuous training on soluble ST2 biomarker in patients with chronic heart failure.

CHAPTER II

LITRATURE REVIEW

Heart Failure (HF) is a clinical syndrome characterized of typical symptoms breathlessness, ankle swelling and fatigue that may be accompanied by signs (e.g. elevated jugular venous pressure, pulmonary crackles and peripheral edema) caused by a structural and/or functional cardiac abnormality, resulting in a reduced cardiac output and/ or elevated intracardiac pressures at rest or exertion (*Ponikowski et al., 2016*).

Heart failure is a syndrome characterized initially by left ventricular dysfunction that triggers countermeasures aimed to restore cardiac output. These responses are compensatory at first but eventually become part of the disease process itself leading to further worsening cardiac function (Yancy et al., 2016).

The American College of Cardiology and The American Heart Association ACC/AHA defines Systolic Heart Failure (SHF) as a complex clinical syndrome resulting from any structural or functional cardiac abnormality that impairs the ability of the ventricle to eject blood with manifestations of dyspnea, fatigue, exercise intolerance and fluid retention leading to splanchnic congestion and/or peripheral edema (Yancy et al., 2013).

Similarly, the ESC defines SHF as a clinical symptom characterized by typical symptoms of breathlessness, ankle swelling and fatigue that may be accompanied by signs of elevated jugular pressure, pulmonary crackles and peripheral edema caused by structural and/or functional cardiac abnormality resulting in reduced cardiac output. The two definitions further distinguish SHF from

diastolic heart failure (DHF), the former resulting from impaired contractile function (defined by depressed ventricular ejection < 40%) while the latter results from impaired ventricular filling, compliance or relaxation (defined by a mildly reduced or preserved ejection fraction > 50%) (*Ponikowski et al., 2016*).

In addition to routine clinical laboratory tests (including natriuretic peptides and cardiac troponins), other biomarkers are gaining attention for their utility in heart failure (HF) management. Among them, soluble ST2 (sST2) a novel biomarker integrating inflammation, fibrosis, and cardiac stress has been included in the 2013 ACCF/AHA guideline for additive risk stratification of patients with acute and chronic HF (yancy et al., 2013).

Soluble ST2 is an interleukin-1 (IL-1) receptor family member, is secreted into the circulation and functions as a "decoy" receptor for IL-33, inhibiting IL-33/ST2 signaling. Blood concentrations of sST2 are increased in various diseases such as inflammatory diseases and heart diseases and are considered a valuable prognostic biomarker in both conditions. Soluble ST2 lacks disease specificity and, therefore, is not a valuable biomarker for the diagnosis of HF. In acute and chronic HF, however, sST2 is strongly associated with measures of HF severity and poor outcome. Several studies in patients with HF indicate that serial measurement of sST2 has prognostic value and could have a potential role in future biomarker-directed therapy (Dieplinger and Mueller 2015).

In the issue of Circulation: Heart Failure, *(Pascual-Figal et al 2018)* presents the first data indicating the production of soluble ST2 protein by organs other than the heart and vessels. Using an experimental model of HF (permanent left anterior descending

occlusion in a rat model); they measured soluble ST2 mRNA in lung, kidney, and liver tissue samples obtained at prespecified time-points. The liver and kidneys did not participate in ST2 production during any of the studied periods. Concentrations of sST2 have been implicated in the presence and severity of heart failure with particular value for prognostication. It was reviewed the use of sST2 as a prognostic biomarker in heart failure, including present and future directions in this exciting area (*Bhardwaj and James 2010*)

Much published work has examined and confirmed the beneficial physiological effects of aerobic physical activity or moderate intensity (55%–70% of maximal heart rate (MHR), rate of perceived effort (RPE) of 11–13 on the Borg scale) continuous training, known as MICT. World Health Organization (WHO) recommends a minimum of 150 min per week of aerobic physical activity at moderate continuous intensity to maintain or achieve health *(Wood et al., 2019).*

Exercise of high submaximal intensity performed in intervals of 1 to 4 minutes, also called high-intensity interval training (HIIT), has been tested in a multiple studies on patients with heart failure with reduced ejection fraction, showing that HIIT was superior to moderate continuous training (MCT) in improving exercise capacity, quality of life, endothelial function, and left ventricular diameter and ejection fraction. The results were better than those observed in previous studies and meta-analyses of patients with chronic heart failure. They also prompted discussions of whether HIIT should be included in standard care of patients with chronic heart failure. *Guidelines for rehabilitation in patients with cardiovascular disease (JCS 2014).*

Despite concerns regarding patient adherence, several studies have shown irrefutable advantages of HIT in patients with cardiac failure. It is interesting that HIT protocols, the total exercise volume, and time commitment have been significantly lower compared to moderate-intensity training, and yet its use still shows various positive physiological benefits that are at least comparable with moderate-intensity protocols. It is also important to note that HIT has been shown to be safe, tolerable, and enjoyable for patients with cardiovascular disease, eliminating any major concerns of an increase in adverse effect risk (*Hussain et al., 2016*).

CHAPTER III PATIENTS AND METHODS

The current study is designed to compare the effect of high intensity interval training versus moderate continuous training exercise on soluble ST2 biomarker level in chronic heart failure patients with New York heart association (NYHA) classification I, II.

Patients:

This study will be carried out on sixty male patients suffering from chronic Heart failure NYHA classification (I & II) with an age range from 50 to 60 years old. The patients will be selected from Aldmerdash hospital, Ain shams university and patients will be randomly assigned into two groups. The purpose, nature and potential risk of the study will be explained to all patients.

Ethical considerations:

- Approval of faculty ethical committee.
- The study procedures will be explained for all participants.
- Confidentiality will be assured.
- An informed consent will be taken from each subject prior to participation (Appendix I).

Criteria for the patient selection:

Inclusion Criteria:

The patient selection will be according to the following criteria:

- They will have chronic heart failure (New York heart association class I& II) systolic left ventricular dysfunction.
- Their left ventricular ejection fraction (LVEF) <40%.
- Medical treatment will be optimized at least three months prior to study entry.
- All patients didn't participate in any rehabilitation programs prior to the study.

Exclusion criteria:

Patients who will meet one of the following criteria are to be excluded from the study:

Signs of acute heart failure, unstable angina or severe • arrhythmia three months prior to enrolment in the study.

Pacemakers. •

Chronic obstructive pulmonary disease.

Other disorders counteracting exercise testing conditions • that limit lower limb mobility (for example, burns, fractures)

Pre-existing neuromuscular diseases (for example • Myasthenia Gravis).

Patients will be assigned into two groups with a group A receiving HIIT and group B receiving MICT, both groups will receive their optimal medical treatment.

All patients will be thoroughly evaluated before and • after treatment protocol application.

All patients will receive their prescribed medical • treatment.

Evaluation

Primary outcome to be measured is soluble ST2 biomarker level **Secondary out come** to be measured is ejection fraction, quality of life and peak exercise response.

Soluble ST2 biomarker

.1

The Presage(®) ST2 Assay

(Critical Diagnostics, CA, USA) is an in vitro diagnostic device that quantitatively measures soluble suppression of tumorigenicity 2 (sST2) in serum and plasma by ELISA (Mueller and Dieplinger 2013).

Procedure: sample will be taken at the cubited vein at the beginning of the program and also at its end.

Echocardiogram.

Left ventricular systolic dysfunction will be assessed using the ejection fraction by 2D simpson method (the percentage of the end diastolic volume ejected during systole).

.2

Resting echocardiographic images will be acquired in accordance with American Society of Echocardiography guidelines by a cardiac sonographer, blinded to group allocation *(Lang et al., 2015).*

Procedure: A commercially available ultrasound system (Vivid S5 or E90, GE Medical Systems, Horten, Norway) equipped with a 2.5-MHz multifrequency phased array transducer will be used to determine the echocardiogram variables by the physician.

3. Minnesota Living with Heart Failure Questionnaire

The questionnaire has 21 items. Assessing the impact of frequent physical symptoms of heart failure. Other items ask about the effects of heart failure on physical and social functions as well as mental and emotional functions. Since treatments might have direct effects on a patient's life in addition to their effects on symptoms and functional limitations of heart failure, questions about side effects of medications, hospital stays and costs of care were included to help measure the overall impact of treatments for heart failure on patients' quality of life.

Procedures: When administering the Minnesota Living with Heart Failure Questionnaire to a subject, the instrument must be

completed fully and it is crucial to explain to the patient why it is important to collect his opinions in order to reduce the number of missing data and therefore maximize the quality of the 10 data collected (Appendix II).

4- Modified Bruce exercise test

A symptom-limited graded treadmill exercise test (GXT) will be carried out prior to the exercise rehabilitation program to tailor the exercise training program using modified Bruce protocol .The following exercise parameters will be assessed: a) Exercise duration, b) estimated achieved metabolic equivalent of task (METs), c) basal heart rate (BHR), d) peak heart rate (PHR) and peak exercise response. The exercise test will be repeated after completion of the 3-month CR program to assess the change in functional capacity of the patients with respect to the fore-mentioned parameters (*Pescatello et al., 2014*).

Procedure:

Exercise will be performed on a treadmill. The leads of the ECG are placed on the chest wall. The treadmill is started at 2.74 km/hr (1.7mph) and at inclinator gradient of 10% after 3 min incline af the treadmill is increased by 2% and the speed increases. The test should be stopped when the subject cannot continue due to fatigue or pain or due to any other medical condition (*Badawy and Muaidi 2019*).

Training

Management procedures

Group A

Patients will receive medical treatment and will be submitted to the cardiac rehabilitation unit receiving HIIT *(pelliccia et al., 2021).*

Frequency: HIIT, MCT will be in 2 supervised sessions per • week for 12 weeks on treadmill.

Intensity: HIIT included 4 minute intervals aiming 60-85% of • heart rate reserve separated by 3 min active recovery period of moderate intensity exercise 40-59% of heart rate reserve.

Duration: The session lasts 30-40 min included warming up • and cooling down at moderate intensity.

Group B

Patient will receive medical treatment and will be submitted to the cardiac rehabilitation program receiving MICT (Mueller et al., 2021).

Frequency: Moderate continuous training is scheduled 2 times • per week for 12 weeks.

Intensity: exercise will be applied on treadmill (40%-59% of • heart rate reserve)

Duration: 30-40 minutes per session.

Safety: all the procedures will be applied inside the cardiac rehabilitation unit.

Only the patients who will complete the 3 month CR program attending $>\!80\%$ of the exercise training sessions will be included in this study.

Data analysis:

The collected data will be statistically analyzed using descriptive statistics (the mean and standard deviation).

The paired t test will be used to determine the significance level • between pre and post physical therapy treatment.

The level of significance < (0.05).

References

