Appendix II

MINNESOTA LIVING WITH HEART FAILURE® QUESTIONNAIRE

The following questions ask how much your heart failure (heart condition) affected your life during the past month (4 weeks). After each question, circle the 0, 1, 2, 3, 4 or 5 to show how much your life was affected. If a question does not apply to you, circle the 0 after that question.

Did your heart failure prevent you from living as you wanted during the past month (4 weeks) by -	No	Very Little				Very Much
 causing swelling in your ankles or legs? making you sit or lie down to rest during 	0	1	2	3	4	5
the day?	0	1	2	3	4	5
making your walking about or climbing stairs difficult?	0	1	2	3	4	5
making your working around the house or yard difficult?	0	1	2	3	4	5
making your going places away from home difficult?	0	1	2	3	4	5
making your sleeping well at night difficult?	0	1	2	3	4	5
making your relating to or doing things with your friends or family difficult?	0	1	2	3	4	5
making your working to earn a living difficult?	0	1	2	3	4	5
making your recreational pastimes, sports or hobbies difficult?	0	1	2	3	4	5
10. making your sexual activities difficult?	o	î	2	3	4	5
making you eat less of the foods you						_
like?	0	1	2	3	4	5
12. making you short of breath?13. making you tired, fatigued, or low on	0	1	2	3	4	5
energy?	0	1	2	3	4	5
14. making you stay in a hospital?	0	î	2 2 2	3	4	5
15. costing you money for medical care?	0	î	2	3	4	5
16. giving you side effects from treatments?	0	î	2	3	4	5
17. making you feel you are a burden to your		•	~			
family or friends?	0	1	2	3	4	5
18. making you feel a loss of self-control		- 2	•			
in your life?	0	1	2	3	4	5
19. making you worry?	0	1	2	3	4	5
20. making it difficult for you to concentrate			~	2		-
or remember things?	0	1	2	3	4	5
21. making you feel depressed?	0	1	2	3	4	5

©1986 Regents of the University of Minnesota, All rights reserved. Do not copy or reproduce without permission. LIVING WITH HEART FAILURE® is a registered trademark of the Regents of the University of Minnesota.

Note: the questionnaire was taken by personal interviewing

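### NYHA classes I and II are pooled with no stratified or blocked allocation, although the protocol ties sST2 to severity: a cheap, minor improvement to the randomisation and the between-arm model

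*Protocol*

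**What the plan says.** Protocol, Chapter III, Patients, describes the sample as "sixty male patients suffering from chronic Heart failure NYHA classification (I & II") and states that "patients will be randomly assigned into two groups". That is all it says about how allocation is done. No sequence type, ratio, block or stratification factor appears, and there is no quota by class.

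The inclusion criteria repeat the mix: "They will have chronic heart failure (New York heart association class I& II) systolic left ventricular dysfunction". They also restrict ejection fraction to below 40%.

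Under Evaluation, "Primary outcome to be measured is soluble ST2 biomarker level". Ejection fraction, quality of life and peak exercise response are secondary. For sST2, the "sample will be taken at the cubited vein at the beginning of the program and also at its end", so each patient has a baseline value.

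Chapter II says of acute and chronic heart failure that "sST2 is strongly associated with measures of HF severity and poor outcome", and makes the same link to severity again a little later. Appendix II gives the Minnesota questionnaire: 21 items scored 0 to 5, with the instruction "If a question does not apply to you, circle the 0 after that question".

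The hypothesis in Chapter I is a difference between the two training types. The Data analysis section names only a paired pre-post t test. The training section limits the study to patients who finish the programme with more than 80% attendance.

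**The concern.** The one patient characteristic that the protocol itself links to its primary outcome is severity. Class is a coarse measure of severity and is recorded for every patient at screening, yet nothing in the allocation uses it. At sixty patients, chance alone can leave one arm with visibly more class II patients. If so, an unadjusted between-arm comparison of post-training sST2 would carry part of the severity difference with it.

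Change scores remove a constant offset between classes, but not a difference in how the classes respond. Unequal response is plausible for quality of life, because a questionnaire item already at 0 cannot improve.

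Allocation is fixed when the first patient is assigned. A separate analysis plan could add a covariate later but could not stratify patients already assigned, so the protocol is the right place for this.

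**Working it through.** The protocol gives no calculation to reproduce. The inputs taken from it are N = 60, NYHA I and II without a quota, sST2 at baseline and end, and a 0.05 level (two-sided assumed). The assumptions are 30 per arm, the class I share, the size of the class difference and a pre-post correlation of 0.6. SDs are within class.

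**1. Chance of an uneven class mix.** With K class I patients among 60 and 30 per arm, the number X in one arm is hypergeometric and the arms differ by |2X − K|. A gap of 20 percentage points is 6 patients of 30.

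- K = 12 (20%): Pr(|2X − 12| ≥ 6) = 0.104
- K = 18 (30%): 0.158
- K = 20 or 40 (33% or 67%): 0.170
- K = 30 (50%): 0.196

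If allocation were an independent coin toss per patient instead, the simulated figures for class I shares of 20%, 30% and 50% are 6%, 10% and 15%.

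**2. Size of the shift from a 20-point gap.** Let class II exceed class I by g SD at baseline and by g + h SD after training, so that h is the class difference in change.

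- Post values: 0.2 × (g + h). With h = 0: 0.10 SD for g = 0.5 and 0.20 SD for g = 1.0. With h = 0.3: 0.16 and 0.26 SD.
- Change scores: 0.2 × h, which is 0 for h = 0 and 0.06 SD for h = 0.3.

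For scale, 30 per arm detects (1.960 + 0.842) × √(2/30) = 0.72 SD with 80% power.

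**3. Type I error.** This was simulated with half of the patients in class I, correlation 0.6 and 8,000 runs per scenario. Over all unstratified runs, every method lies between 4.6% and 5.4%. Restricted to runs with a gap of at least 20 points (about 1,500 per scenario, simulation error about 0.6 points):

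| g, h | Post value | Change | Baseline-adjusted | Baseline + class |
|---|---|---|---|---|
| 0.5, 0 | 5.8% | 4.9% | 4.1% | 4.5% |
| 0.5, 0.3 | 7.8% | 5.2% | 6.4% | 5.4% |
| 1.0, 0 | 10.7% | 5.1% | 6.8% | 4.7% |
| 1.0, 0.3 | 14.2% | 6.4% | 7.9% | 5.4% |

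**4. Where the precision comes from.** With equal classes, let Vb = 1 + 0.25g², Vy = 1 + 0.25(g + h)² and C = 0.6 + 0.25g(g + h). The residual variance is Vy for post values, Vy − C²/Vb with baseline adjustment, and 1 − 0.6² = 0.64 with baseline and class.

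- g = 1, h = 0: 1.25, then 1.25 − 0.85²/1.25 = 0.672, then 0.64. Baseline cuts the standard error by 1 − √(0.672/1.25) = 27%; class cuts it by a further 1 − √(0.64/0.672) = 2%.
- Over the four scenarios above, class adds 1%, 4%, 2% and 7%, before the small loss from one degree of freedom and from any imbalance.

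Simulated power for a true 0.65 SD difference at g = 1, h = 0 agrees. Without stratification it is 0.60 (post), 0.79 (change), 0.85 (baseline-adjusted) and 0.86 (baseline and class). With stratification it is 0.60, 0.79, 0.84 and 0.86.

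**The case against.** The strongest reply is that unstratified randomisation of sixty patients is not an error. A valid between-arm test already allows for chance imbalance, covariates are commonly left to an analysis plan, and the baseline sST2 sample absorbs most of any severity offset. The figures above bear this out, and it is why the point is small. What remains is that stratification can only be set before allocation, uses a variable already collected and costs almost nothing.

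Four stronger readings are tempting, and the documents do not support them.

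- **That the protocol prescribes simple randomisation.** It leaves the method open. The accurate statement is that no stratification or blocking is specified.
- **That an imbalance would mimic or hide a training effect in general.** Randomisation keeps the average type I error near 5%. The distortion belongs to the single realised trial, and mainly to unadjusted post values or to classes that respond differently.
- **That sST2 follows a different course in class I and class II.** Chapter II speaks of an association with severity. It does not compare these two classes and says nothing about change under training. The sample is also narrowed by ejection fraction, sex, age and stable treatment.
- **That class I patients sit at the floor of the quality-of-life scale.** No scores by class are given. The instruction to circle 0 is a scoring rule, and items such as cost of care or worry need not follow class. A floor is plausible, but undocumented, and quality of life is a secondary outcome.

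It is also fair to say that stratifying at entry does not guarantee balance in the analysed set, because patients below the attendance threshold are dropped. That favours keeping class in the model.

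**Conclusion.** The point holds as a minor design improvement. Classes I and II are pooled, no stratification or blocking is specified, and the protocol itself links the primary outcome to severity. With 30 per arm and 20% to 67% class I, a class gap of 20 points or more has a probability of about 10% to 20%.

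On average there is no type I error problem. Given such a gap, the error of an unadjusted post-value comparison is about 6% to 14% under the assumed class differences, against about 5% with baseline and class in the model. For sST2, stratification by itself adds essentially no power once baseline is used.

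The class share, the class differences and the arm sizes are assumptions shown as ranges or stated; the correlation of 0.6 is a single assumed value.

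**What to change.** In Chapter III, Patients, specify 1:1 allocation stratified by NYHA class (I versus II) in permuted blocks of varying size. In the between-arm comparison of sST2 and of each secondary outcome, include NYHA class together with the baseline value of that outcome. The Data analysis section names no between-arm comparison at present, so the comparison itself has to be stated there or in the analysis plan. If quality of life is shown by class, label it descriptive only.

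With complete blocks the class gap disappears. An unfinished last block of, say, 4 or 6 can leave at most 2 or 3 patients' difference in a stratum.

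The cost is two randomisation lists instead of one and one degree of freedom. No new data are needed. Because exclusion for low attendance can partly undo the balance, class should stay in the model even after stratified allocation.

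### The three-month stability window omits myocardial infarction, coronary revascularisation and cardiac surgery, so recovery from a recent cardiac injury could pass for a within-arm training effect on sST2 and add noise to the arm comparison

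*Protocol*

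**What the plan says.** The same event window appears twice, under Delimitations and under Exclusion criteria in Chapter III. It covers "Signs of acute heart failure, unstable angina or severe" arrhythmia, and its time limit reads "arrhythmia three months prior to enrolment in the study". The rest of each list concerns pacemakers, chronic obstructive pulmonary disease, disorders limiting lower limb mobility and neuromuscular disease. Myocardial infarction, coronary revascularisation and cardiac surgery appear in neither list.

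The nearest guards elsewhere are:
- the inclusion criterion "Medical treatment will be optimized at least three months prior to study entry";
- the requirement for chronic heart failure in NYHA class I or II, with ejection fraction below 40%;
- no earlier rehabilitation programme;
- under Basic Assumptions, a complete medical history, physician referral and "homodynamic stability without need for vasoactive drugs".

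On the biomarker, the Introduction states: "It has been suggested that sST2 is produced by both cardiac fibroblasts and cardiomyocytes in response to injury or stress". Chapter III makes sST2 the primary outcome and ejection fraction a secondary one. Blood for sST2 is drawn at the start and at the end of the 12-week programme. Both groups train. The only test named under Data analysis is a paired t test of pre against post values, at the 0.05 level.

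**The concern.** The window evidently aims to keep out patients whose hearts were recently unstable. It names unstable angina but not infarction or a cardiac procedure. A man with long-standing heart failure on unchanged drugs, in NYHA class I or II, who had an elective bypass operation six weeks before entry meets every criterion as written.

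If his sST2 is raised by the recent injury and settles during the programme, the whole change lies between the only two samples. With no untrained arm and a pre/post test, nothing in the named analysis separates that recovery from an effect of training. The comparison between arms is less exposed, because randomisation spreads such patients evenly on average, but the extra spread still costs precision.

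**Working it through.** **Step 1: does any other criterion close the gap?**
- Optimised treatment for three months concerns medication. It will screen out some recent infarctions, where drugs were changed, but not a procedure in a man whose drugs stayed the same.
- Chronic heart failure, NYHA class and ejection fraction describe current status, not recent events.
- Absence of earlier rehabilitation does not rule out a recent event.
- Haemodynamic stability is listed as an assumption and carries no time limit.

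None of these excludes a recent infarction, revascularisation or operation by its wording.

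**Step 2: inputs.** The protocol gives 60 patients but no effect size, SD, power or allocation ratio, so there is no figure of its own to reproduce. The following are assumptions:
- SD of the change in log sST2 in stable patients: 0.30 to 0.40;
- extra fall d in a recently injured patient: 0.5 log units, since exp(-0.5) = 0.61, a fall of about 39%;
- proportion recently injured, p: 2%, 5% or 10%, which is about 1, 3 or 6 of 60 patients.

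**Step 3: noise in the randomised comparison.** Mixing the two kinds of patient adds variance p(1-p)d² in each arm, so the SE ratio is sqrt(1 + p(1-p)d²/SD²). This ratio does not depend on the number per arm.

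| p | Added variance | SE ratio, SD 0.40 | SE ratio, SD 0.30 |
|---|---|---|---|
| 2% | 0.02 × 0.98 × 0.25 = 0.0049 | 1.015 | 1.027 |
| 5% | 0.05 × 0.95 × 0.25 = 0.0119 | 1.036 | 1.064 |
| 10% | 0.10 × 0.90 × 0.25 = 0.0225 | 1.068 | 1.118 |

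The worst cell has a variance ratio of 1 + 0.0225/0.09 = 1.25, so 60 patients would carry the information of 60/1.25 = 48. The mildest has 1 + 0.0049/0.16 = 1.031, equivalent to about 58.

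**Step 4: shift within an arm.** The expected mean change moves by p × d = 0.010, 0.025 or 0.050 log units at 2%, 5% or 10%, with no training effect at all.

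To see what this does to a paired test, 40,000 trials were simulated with 30 patients per arm (assumed, as no ratio is stated), no training effect and a two-sided 0.05 level. A fraction f of patients had a spontaneous fall of s SDs. The 0.5 log fall above corresponds to s = 0.5/0.40 = 1.25 up to 0.5/0.30 = 1.67, so the two right-hand columns are the closest, and the upper end lies slightly beyond the grid.

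| f | Paired test, s = 0.5 | s = 1.0 | s = 1.5 |
|---|---|---|---|
| 0% | 5.0% | 4.9% | 5.0% |
| 10% | 5.8% | 7.6% | 10.2% |
| 20% | 8.2% | 16.0% | 26.5% |

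The two-sample test between arms rejected in 4.8% to 5.2% of trials in every scenario run. Recently injured patients therefore distort the within-arm test and leave the false-positive rate of the arm comparison intact.

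**The case against.** The strongest reply is that the residual gap is small. A patient must have had a recent event with no signs of acute heart failure, no change in drugs and only mild symptoms, and must also pass history-taking and physician referral. Nothing in the documents shows that such patients are more than rare. At 2% prevalence the loss of precision is 1.5% to 2.7%. This stands, and it limits the size of the point. It does not remove the gap, because unwritten clinical judgement at screening is not a reproducible criterion.

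A second reply is that reading any time trend as a treatment effect is a weakness of a paired test without an untrained arm, which an eligibility edit cannot cure. That is also right. The edit removes one avoidable source of trend, not the weakness itself.

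A reader might also infer more than the documents support:
- **That injury is known to drive sST2.** The protocol says only that production after injury or stress has been suggested. It does not say that sST2 falls over 12 weeks after an infarction, a revascularisation or an operation, or that the three have the same course.
- **That the protocol documents spontaneous recovery.** The Introduction mentions "favorable cardiac chambers remodeling in post-infarction", but that sentence describes remodelling induced by exercise.
- **That the randomised comparison is biased.** Allocation is random, so the cost there is variance only. Chance imbalance in the number of recently injured patients is that same variance and should not be counted as a further harm.

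**Conclusion.** The omission is real in both lists, and no other criterion closes it by its wording. Its main consequence is for the within-arm pre/post test, the only test the protocol names, where spontaneous recovery could be read as a training effect. If 10% of patients were recently injured, the false-positive rate of that test would be about 6% to 10% instead of 5%, for falls of 0.5 to 1.5 SDs. For the randomised comparison the consequence is lost precision: a standard error about 2-3% larger at 2% prevalence and 4-12% larger at 5-10%.

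All of these figures rest on assumed prevalence, fall and SD. The documents give none of them, and they do not show how many such patients would enrol. The point does not undermine the trial, but it should be corrected because the remedy is cheap.

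**What to change.** In both exclusion lists, extend the existing pre-enrolment stability window to cover myocardial infarction, coronary revascularisation and cardiac surgery. The investigators should confirm the interval, which is a clinical decision. Keep the wording identical in the two lists.

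The cost is one line in each list, checked from the medical history already taken for every patient. The downside is that a few patients are deferred.
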